### **Causes of Death Register (NOR)**

The Causes of Death Register provides data on dates and causes of death with PIN, sex, age, place of residence and causes of death reported by ICD-10 diagnosis codes.

## Drugs and Pregnancy Project (FIN)

DPP will be a data source for the Finnish data regarding information on maternal MS diagnosis, MSDMDs, TOPFAs, live births, stillbirths, and MCAs. The purpose of the Finnish DPP, initiated in 2003, is to evaluate the pattern of drug use during pregnancy and estimate the effect of drug use on pregnancy outcomes. The research data are based on information obtained from the Finnish national health registers: the MBR, the Register on Induced Abortions and the Malformation Register, all maintained by THL (Artama et al. 2011). Information on maternal drug use and drug reimbursements is obtained from the Prescription Register and the Register on Reimbursed Medications, both maintained by the SII. The research database enables evaluation of the frequency and type of maternal drug use during pregnancy retrospectively from the year 1996 onwards (at the time of data extraction until the end of 2014). Drug purchases are recorded covering a time period from one month prior to pregnancy to the end of pregnancy in the DPP.

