**Table 2: List of relevant data sources in different countries.**

Finland		
Outcome	Register	Register holder
Ectopic pregnancies	Patient Register (Care Register for Health Care)	National Institute for Health and Welfare (THL)
Spontaneous abortions	Patient Register (Care Register for Health Care) (of previous pregnancies from DPP)	THL
Elective terminations	DPP	THL
Stillbirths with and without foetal defects	DPP	THL
Live births with and without congenital anomaly	DPP	THL

Exposure	DPP National Prescription Register National Reimbursement Register	THL Social Insurance Institution (SII)
MS population	DPP, Patient Register (Care Register for Health Care)	THL
General population	Population Register	Statistics Finland (SF)
Sweden		
Outcome	Register	Register holder
Ectopic pregnancies	Patient Register	National Board of Health and Welfare
Spontaneous abortions	Patient Register	National Board of Health and Welfare
Elective terminations	not recorded in SWE	N/A
Stillbirths with and without foetal defects	MBR	National Board of Health and Welfare
Live births with and without congenital anomaly	MBR	National Board of Health and Welfare
Exposure	Prescribed Drug Register	National Board of Health and Welfare
MS population	Patient Register, MS Register	National Board of Health and Welfare
General population	Population Register	Swedish Tax Agency
Norway		
Outcome	Register	Register holder
Ectopic pregnancies	Patient Register	Norwegian Directorate of Health
Spontaneous abortions	Patient Register (of previous pregnancies in MBR)	Norwegian Directorate of Health Norwegian Institute of Public Health (NIPH)
Elective terminations	MBR	NIPH
Stillbirths with and without foetal defects	MBR	NIPH
Live births with and without congenital anomaly	MBR	NIPH
Exposure	Prescription Register	NIPH
MS population	MS Register	Helse Bergen
General population	Population Register	Statistics Norway

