### 9.4 Variables

**Exposures:** Maternal MS and related medication exposure before and during pregnancy are the basis of the exposure status of the study subjects in this study.

Pregnancies are considered unexposed if no MSDMDs of interest have been used within three months (except six months for mitoxantrone and cladribine) prior to LMP or during pregnancy. As the maximum reimbursable amount per purchase is the supply for three months of treatment, a pregnancy is defined as unexposed to MSDMDs if there are no purchases of MSDMDs within six months (except nine months for mitoxantrone and cladribine) prior to LMP or during pregnancy. Otherwise a pregnancy is defined as exposed to MSDMDs. Similarly, a pregnancy is defined as unexposed to IFN- $\beta$  if there have been no purchases of IFN- $\beta$  containing medications within six months prior to LMP or during pregnancy and otherwise a pregnancy is defined as exposed to IFN- $\beta$ .

The following MSDMDs and their ATC codes are included in this study: IFN- $\beta$ -1a (L03AB07), IFN- $\beta$ -1b (L03AB08), Peg IFN- $\beta$ -1-a (L03AB13), human normal immunoglobulin (J06BA02), cyclophosphamide (L01AA01), methotrexate (L01BA01, L04AX03), cladribine (L01BB04), mitoxantrone (L01DB07), alemtuzumab (L01XC04), glatiramer acetate (Copaxone®) (L03AX13), leflunomide (L04AA13), natalizumab (L04AA23), fingolimod (L04AA27), teriflunomide (L04AA31), azathioprine (L04AX01), dimethyl fumarate (N07XX09).

**Table 3: More detailed information on individual MSDMD agents, including information on availability and reimbursement in FIN, SWE and NOR.**

MSDMD agent	ATC code	Reimbursed in FIN in Jan 2015 (yes / no) 	Marketing authorisation date			Administration in hospital only 
			FIN	SWE	NOR	
IFN- $\beta$ natural	L03AB02		no	no	no	
IFN- $\beta$ -1-a	Avonex ®	yes	13.3.1997	13.3.1997	5.7.2002	no
	Rebif ®		4.5.1998	4.5.1998	19.8.2003	no
IFN- $\beta$ -1-b	Betaferon ®	yes	30.11.1995	30.11.1995	1.9.2006	no
	Extavia ®		20.5.2008	20.5.2008	20.5.2008	no
Peg IFN- $\beta$ -1-a	Plegridy ®	yes	18.7.2014	18.7.2014	18.7.2014	no
intravenous immunoglobulin	J06BA02	no	16.10.1991	10.10.1981	9.10.1996	yes
cyclophosphamide	L01AA01	no	4.6.1986	28.4.1959	6.4.1959	injection yes tablet no
methotrexate	L01BA01	yes  / no 	25.2.1981	23.6.1964	14.4.1971	tablet no
	L04AX03					infusion yes injection yes/no 

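### The protocol does not say which Finnish source covers MSDMD purchases from six months to one month before LMP, and one source it names, the DPP, does not hold them

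*Protocol*

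**What the plan says.** Section 9.4 sets the rule. A pregnancy is unexposed to MSDMDs when there are "no purchases of MSDMDs within six months (except nine months for mitoxantrone and cladribine) prior to LMP or during pregnancy". The IFN-β rule uses the same period: no purchases of IFN-β "containing medications within six months prior to LMP or during pregnancy". The reason given is that "the maximum reimbursable amount per purchase is the supply for three months of treatment". A three-month exposure period before LMP therefore needs six months of purchase data.

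Section 9.3.1.2, under Drugs and Pregnancy Project (FIN), states: "DPP will be a data source for the Finnish data regarding information on maternal MS diagnosis, MSDMDs, TOPFAs, live births, stillbirths, and MCAs". The same paragraph ends: "Drug purchases are recorded covering a time period from one month prior to pregnancy to the end of pregnancy in the DPP".

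Two other places bear on the Finnish source:

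- Table 2 lists three items for Finnish exposure, "DPP National Prescription Register National Reimbursement Register", with THL and the Social Insurance Institution (SII) as holders.
- Section 9.3.1.1, under Prescription Registers, takes MSDMD exposure before and during pregnancy from the Prescription Registers in all three countries, and adds in brackets that in Finland this information is linked to the DPP. It dates the Finnish register from 1994, two years before the Finnish study period begins.

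No section says which source supplies Finnish purchases from six months to one month before LMP. The exposure paragraphs of section 9.9 deal with drugs given in hospital and with reimbursement and market status, not with this limit.

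**The concern.** The window held in the DPP is five months shorter than the window that the exposure rule needs. The text leaves open that the DPP purchase variable will be used, because the DPP is named for MSDMDs and the Finnish prescription data are described as linked to it.

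A short window can only lose exposures. A woman whose last IFN-β purchase was two months before LMP, and who used that supply into early pregnancy, is exposed under section 9.4 but has no purchase in the DPP window. She would be counted in cohorts 3 and 4, the comparators for the two primary comparisons. A woman with an IFN-β purchase inside the window and another MSDMD purchase outside it would be counted as IFN-β only (cohort 1). Finland would in effect apply a one-month rule while Sweden and Norway apply a six-month rule. Adjustment for country does not undo misclassification within Finland. The unexposed prevalence requested by the CHMP would be affected as well.

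**Working it through.** **1. The plan's own figure.** Inputs from section 9.5: cohort 1 n1 = 294, cohort 3 n0 = 1270, baseline p0 = 24/331 = 0.0725, two-sided 5%, 80% power. The two-proportion normal approximation, with pooled variance under the null, gives

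power = Φ{ [ (p1 − p0) − 1.96·√(p̄(1−p̄)(1/n1 + 1/n0)) ] / √(p1(1−p1)/n1 + p0(1−p0)/n0) }.

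With p1 = 1.72 × 0.0725 = 0.1247 and p̄ = 0.0823, this is Φ{(0.0522 − 0.0349)/0.0206} = Φ(0.84) = 80%. The stated detectable relative risk (RR) of 1.72 is reproduced. The point does not make that figure wrong.

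**2. Window shortfall.** 6 − 1 = 5 months for IFN-β. A three-month supply bought between three months and one month before LMP lasts until between LMP and two months after it, and is not in the DPP. Section 9.2.4 treats LMP as the beginning of pregnancy, and the DPP window is read the same way here.

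**3. Share missed, by time of stopping.** Assume regular three-month purchases, so that the last purchase is uniform over the three months before stopping. Let s be the stopping time in months relative to LMP. With the DPP window, a woman is missed if her last purchase was earlier than −1, so the share missed is (2 − s)/3, limited to 0–1. With the six-month window it is (−3 − s)/3, which is 0 for every s ≥ −3.

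| Stop (months from LMP) | Missed, DPP window | Missed, six-month window |
|---|---|---|
| −3 to −1 | 100% | 0% |
| −0.5 | 83% | 0% |
| 0 | 67% | 0% |
| +1 | 33% | 0% |
| +2 or later | 0% | 0% |

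The six-month rule does what it was built to do. The one-month window does not.

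**4. Effect on the pooled primary comparison.** The documents give no distribution of stopping times, so the share m of Finnish cohort 1 pregnancies missed is an assumption. The number moved is 294 × (777/1671) × m. With p0 = 0.073 and the same true RR of 1.72 in every exposed woman, risk in the exposed is 0.073 × 1.72 = 0.1256, and comparator risk is (1270 × 0.073 + moved × 0.1256)/(1270 + moved).

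| m | Moved | Observed RR | Power (80% before) |
|---|---|---|---|
| 10% | 14 | 1.71 | 78% |
| 25% | 34 | 1.69 | 75% |
| 50% | 68 | 1.66 | 68% |
| 67% | 92 | 1.64 | 63% |

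Example for m = 50%: (92.7 + 68.4 × 0.1256)/1338.4 = 0.0757, and 0.1256/0.0757 = 1.66. Most of the power loss comes from the smaller cohort 1, not from the dilution of the RR.

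**The case against.** The DPP is called one data source, not the only one. Table 2 puts the National Prescription Register beside it, and section 9.3.1.1 takes exposure from the Prescription Registers. The plan also could not be carried out on DPP purchases alone. Finnish spontaneous abortions and ectopic pregnancies come from the Patient Register, duration of MS treatment is a candidate covariate, and section 9.7.6 asks for earlier treatment durations that no one-month window can give. The DPP sentence may simply describe an existing database, with extraction windows left to the data request.

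This stands as far as it goes: a correct extract is possible and may well be intended. It does not settle the point, because the protocol names two sources with different coverage for the variable that defines its cohorts and does not say which one governs.

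Four stronger readings are tempting but not supported:

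- **That Finnish exposure will be misclassified.** This follows only if DPP purchases are used for cohort assignment, and no section says so.
- **That the RR falls to about 1.63–1.54.** Those figures are for Finland alone, with 777 × 0.22 = 171 exposed, 777 × 0.76 = 591 unexposed, and about 50 to 115 missed. Section 9.7 pools the countries.
- **That bias towards 1 is certain.** It rests on equal risk in all exposed women. Those who stop before LMP are missed most often. If their risk were close to that of unexposed women, moving them out of cohort 1 need not dilute the RR.
- **That the nine-month window for mitoxantrone and cladribine is also lost.** Table 3 lists both as not reimbursed in Finland, so the Finnish register does not show them at any look-back.

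**Conclusion.** The point holds as an unreconciled conflict within the protocol. A named Finnish source of MSDMD data covers one month before pregnancy, the rule needs six, and no text assigns the missing five months to a source or lists the limit. The harm is conditional on the extract used, in the country expected to supply 777 of 1671 pregnancies (46%).

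Under the assumptions shown (regular three-month purchases, 10% to 67% of Finnish cohort 1 missed, one common effect), the pooled RR would be only modestly diluted, and the loss of power would be larger. That range is illustrative, because stopping times are not given. The 22% and 24% exposed shares in section 9.5 come from Finnish data whose look-back is also not stated, so they may be too low if it was one month.

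The matter needs settling before the data request, because a too-narrow extract may not be correctable at analysis.

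**What to change.** In section 9.3.1.1 (Prescription Registers), the Drugs and Pregnancy Project paragraph and Table 2, state that:

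- Finnish MSDMD purchases for the full section 9.4 window before LMP, to the end of pregnancy, are extracted directly from the SII National Prescription Register;
- this applies to every pregnancy event, including spontaneous abortions and ectopic pregnancies;
- the DPP purchase variable is not used for cohort assignment.

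Write the same window into the Finnish data permit request, which section 6 schedules for one month after registration. If the full window cannot be obtained, list the limit in section 9.9 and show the Finnish results separately as a sensitivity analysis. Leaving Finland out of the main analysis would be out of proportion to the problem.

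The cost is a few sentences and a wider extract from a register that is already listed and predates the study period.

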### 9.3.2 Validity of the data sources

The Nordic national health registers have a population-wide coverage within each country, and the overall quality of the registers is high. The large size of the health register databases of these countries enable the precise estimates of number of different health indicators, and combined together, they also enable evaluation of rare exposures and outcomes. Use of PINs increases the validity of the information, and the register-based method helps to avoid certain biases, such as recall or reporting bias.

#### 9.3.2.1 MS diagnosis and Exposures

##### MS diagnosis

The Swedish MS Register includes information on approximately 15 000 patients (as in September 2014), with the coverage of about 70% of MS patients in SWE (Ludvigsson et al. 2011). The diagnostic accuracy for patients included in the Swedish MS Register is over 90% (Bahmanyar et al. 2009).

The Register on Special Reimbursement (FIN) includes all the patients who are entitled for special refunds of medicine expenses based on their chronic condition, including MS diagnosis. In practice, only persons who refuse the special reimbursement are excluded from the register. The proportion of these cases is very low, as usually costs for chronic disease related drugs are high.

##### Exposure to MSDMDs

The Prescription registers in FIN, SWE and NOR cover the whole population, and completeness and accuracy of the registers on reimbursed medications is high (Furu et al. 2009, Furu 2008, Wettermark 2007). For quality assurance, a number of routine data checks are carried out frequently in these registers to identify possible errors or inconsistencies in registers in FIN, SWE and NOR. In FIN the register on reimbursed medications comprises all purchases of medicines directly reimbursed upon purchase at the pharmacies (e.g. 99% in 2007) (National Agency for Medicines and Social Insurance Institution, 2007).

However, there are some limitations to the data collected on exposure:

- Patient-level data on drug use in hospitals and other institutions such as outpatient clinics are not collected routinely in the Prescription Register in FIN, SWE, or NOR, creating observation gaps (Furu et al. 2009). Some drugs are dispensed only through outpatient clinics (for example, antiretroviral drugs), and some new drug groups including some biological drugs (for example, infliximab) are mainly administered in hospitals, and are therefore not usually included in the prescription databases (Table 3). Nonetheless, in FIN information on patients who have a special reimbursement, for example, intramuscular injection, and who want to be injected by a healthcare professional, is included in the prescription register as the patient buys the medicine from pharmacy (personal communication with [name], SII on Finland Jan 5, 2015). However, infusion medicines are always obtained from the hospital pharmacy, and therefore information is not included in the Prescription Register (see section 9.7.6 Sensitivity analyses).

### 9.3.2.2 Pregnancy outcomes

#### Medical Birth Register

The MBR data are collected from all maternity hospitals in FIN, SWE and NOR. Data are checked, and any data that are missing or inferred to be incorrect are confirmed by contacting the treating hospitals on maternity hospital records. Furthermore, these data are supplemented from birth and death certificates. Information on perinatal deaths (stillbirths or deaths during the first week of life) is revised and supplemented from the Causes of Death Register. After these additions, the statistics in practice have coverage of 100% of births. According to data quality studies, the majority of the register content corresponds well or satisfactorily with hospital record data depending on the type of information (Teperi 1993, Gissler et al. 1995, Gissler 2010). There have been changes to the data content of the MBRs in order to improve reliability of the register. Also, updates of the notification forms have been conducted to bring the collected information more in line with current care practices.

Validation of MBR variables for specific studies has been carried out in all Nordic registers, but they cover different periods and have only been applied to selected conditions (Kristensen et al. 1996, Gissler & Shelley 2002, Klemmensen et al. 2007, Baghestan et al. 2007). These validation studies have been important for each specific study but are of less value for validating general birth registration details, since the true (correct) values do not replace missing or erroneous variables in the medical birth registers, nor do they apply to changes in coding that might have occurred. The results from the validation studies have been used to improve notification routines and quality controls (Langhoff-Roos et al. 2014). Some variables may be over-reported to patient registers, with implications for the medical birth registers that use the general patient registers based on admission data as a primary source.

#### Congenital malformations

The Finnish Malformation Register receives data on congenital anomalies from hospitals, healthcare professionals and cytogenetic laboratories. It also draws data from the MBR, the Patient Register for Health Care (including Information on Outpatient Services in Specialized Health Care), the Register on Induced Abortions, and the Register of Visual Impairment, all maintained by THL, as well as from the data provided by the National Supervisory Authority for Welfare and Health (Valvira), and from the Causes of Death Register, maintained by SF. The diagnoses obtained from these data sources are confirmed by contacting the hospitals that have given treatment to the infant/foetus. Although the Register mainly collects data from the first year of the infant for monitoring, it also collects data on subsequently detected congenital anomalies for statistics and research. Data check-ups are made regularly, missing cases and case-specific data are added from the MBR, for instance, and any unclear cases and diagnoses are checked and ascertained by contacting the treating hospitals.

The data content and the data collection practices of the Malformation Register were revised in 1985, 1993 and 2005. From 1993 onwards the data coverage can be regarded as very good although there have been no coverage analyses since the 1993 revision. The prevalence of cases with congenital anomalies corresponds to the normal prevalence described in the literature and reported internationally. The prevalence rates of different types of congenital anomalies have also been consistent with the findings of other national and international studies on congenital anomalies. Since 2005, data on congenital malformations have also been derived from the statistics on information on Outpatient Services in Specialized Health Care, which has further improved the total coverage of the Malformation Register to some extent.

### Elective terminations of pregnancy

Information on TOPFA and abortions due to other reasons will be obtained from the DPP (FIN) and MBR (NOR). The Finnish Abortion Register, which is the data source for the DPP regarding pregnancy terminations, collects data on all terminations performed in FIN since 1977. The national abortion legislation requires permission with a legal indication for terminating a pregnancy. The data of the Abortion Register are obtained from hospitals and Valvira. The information is completed with information from the national Hospital Discharge Register. More than 99% of all elective TOPs (regardless of reason of the termination (maternal social or health related, foetal related health) registered in hospital records are included in the Abortion Register (Gissler et al. 1995, Gissler et al. 1996). In NOR, abortions are included in the MBR from 12 GW onwards. SWE does not have a register on abortions.

### Spontaneous abortions and ectopic pregnancies

Information on spontaneous abortions and ectopic pregnancies will be obtained from the Patient Register. The quality of the data of the Patient Registers is dependent on the quality of the master data that is registered by the sector. According to validity studies focused on the quality of the Swedish (Ludvigsson et al. 2011) and Finnish (Sund 2012) patient register data comparing the data to external information sources, the overall completeness and accuracy seemed to vary from satisfactory to very good in these registers. In the Finnish study more than 95% of discharges could be identified from the register (Sund 2012). The positive predictive value (PPV) for common diagnoses was between 75-99% (Sund 2012). Correspondingly, the PPV varied between the diagnoses, but was generally between 85-95% in the Swedish study (Ludvigsson et al. 2011). No specific validity studies have been conducted regarding information on maternal diagnoses of spontaneous abortions or ectopic pregnancies included in the Patient Registers.

#### 9.3.3 Linkage methods

Study permit approvals and access to the study data will be applied for by EPID Research in FIN and by academic collaborators in SWE and NOR. After receiving the permits, EPID Research and the collaborators will send data requests to the data holders, who identify the study population and use the unique PINs to extract all the relevant data for the study population. The data holders will also create a unique dummy study identification number (SID) for each PIN. EPID Research will then receive the data where the PINs have been replaced by SIDs and these will be used for data linkage at the patient level. Therefore, the researchers at EPID Research have access to anonymous data only.

